Baseline differences between the treatment arms in demographic and other potential prognostic variables were examined using chi-square analyses for discrete variables (if prevalence >10% in the treatment arm with the lower prevalence, or Fisher's exact test if not) and t-tests for continuous variables. Prior to data analysis, all major variables were screened for inconsistent or abnormal values. Continuous measures were assessed for skewness and outliers (based on model residuals); no data transformations were necessary to meet modeling assumptions of normality and homogeneity of variance. A two-tailed p-value <.05 was considered evidence of statistical significance for the primary and secondary outcomes. Our primary and secondary analyses used generalized linear mixed-effects models (GLMMs). GLMMs can easily accommodate nesting of repeated observations within subjects, include all who complete at least one assessment (including the baseline assessment), and are the preferred method to analyze longitudinal data (Hamer and Simpson, 2009). Despite our best efforts to retain participants, we expected dropouts (subjects who are lost to follow-up or withdraw early from the study). We attempted to perform all scheduled assessments for subjects who were withdrawn from the protocol and provided financial incentives for participation in assessments. Our intent-to-treat sample included all randomized patients who completed at least one assessment, making our primary and secondary analyses intent-to-treat analyses. We also performed "per protocol" analyses. Our per protocol population included all randomized patients who completed the baseline and post-treatment assessments, and who did not initiate prohibited treatment during the study. We repeated our GLMM analyses using the per protocol sample. Dropout, study withdrawal, and loss to follow-up was tabulated by reason and treatment arm. Analyses were conducted to ascertain to what extent dropouts were nonrandom, and, if so, what factors were associated with dropout. To evaluate potential attrition bias, study dropouts were compared to study completers.

A. Specific data variables collected for the study (e.g., data collection sheets)

Specific variables that were collected and their timeline are presented above in Table 1 and described in the Study Procedures section.

B. Study endpoints

Primary endpoint: Difference in BDD severity (BDD-YBOCS) at the end of treatment/waitlist period.

Hypothesis 1: Participants receiving app-CBT will have greater improvement in BDD-YBOCS scores than those in the waitlist condition at treatment endpoint (week 12).

Secondary endpoints: Difference in secondary clinical outcomes at the end of treatment/waitlist period

Hypothesis 2: Participants who receive app-CBT will have greater improvement on secondary clinical outcome measures (i.e., depression (QIDS-SR), delusionality (BABS), functional impairment (SDS), and quality of life (Q-LES-Q)) than those in the waitlist condition at treatment endpoint (week 12).

C. Statistical methods

Primary endpoint: Preliminary efficacy for reducing BDD symptom severity

Analysis:

The primary outcome model was a hierarchical mixed model (i.e., GLMM) that included time (categorical; baseline, mid-point, and end-of-treatment), treatment (app-CBT vs. waitlist), and their interaction as fixed effects, and modeled time as a repeated measure using either an autoregressive (AR1), Toeplitz, compound symmetry, or unstructured covariance matrix, based on best fit determined by AIC and BIC. The main hypothesis test was based on a specific contrast of treatment difference at week 12. Because these analyses included all subjects who were randomized and completed at least one assessment, it was an intent-to-treat analysis. These analyses included only the 3 assessments from baseline to post-treatment and did not include the follow-up (FU) assessments, because treatment response could be affected by subjects seeking other treatments during the FU period. Between-group effect sizes were calculated using Cohen's *d*. This analysis was then repeated using the per-protocol sample.

In addition to the analyses specified above, we described the proportion of subjects in each treatment arm who achieved response, where response was defined as a 30% or greater reduction in BDD-YBOCS score from baseline to end of treatment (week 12). This empirically derived cut-off of 30% reflects clinically significant improvement and is widely used in BDD treatment studies (Phillips et al., 1997). While no formal comparison was made between treatments, the reporting of response rates is clinically useful and will facilitate comparison to other studies in the field. We reported response as observed (excluding subjects with missing data at week 12).

Secondary endpoint: Preliminary efficacy for secondary outcomes

Analysis:

We used the same hierarchical mixed model approach as described for the primary endpoint to examine significant differences in secondary outcome measures (i.e., depression severity, delusionality, functional impairment, and quality of life) at posttreatment for treated participants compared to waitlist control participants. We did not adjust for multiple testing among secondary outcomes based on the recommendation of Cook and Farewell (1996), who argue that multiplicity adjustments are not necessary if separate test results are interpreted marginally and address different aspects of the patient experience and decision-making process rather than alternative assessments of efficacy.

D. Power analysis

Pre-COVID-19, the sample size required to test a significant symptom severity difference between the app-CBT and the waitlist control conditions at the end of treatment was estimated to be $n=64$ ($n=32$ per group). The sample size estimates were based on a single degree of freedom contrast in an ANOVA design, implemented in SAS for Windows version 9.4. The power model used a two-sided alpha=0.05, a power of 0.90, equal allocation of participants into both treatment arms (app-CBT vs. waitlist), and an anticipated effect size of 0.9. We further assumed a drop-out rate of 15% by the end of treatment. This anticipated effect size of the app-CBT is in the range of effect sizes calculated using the published estimate of a waitlist control group BDD-YBOCS mean after 12 weeks (source: Wilhelm et al., 2014), compared to either the combined site mean at week 12 in an in-person CBT treatment study for people with BDD ($d=0.93$; Wilhelm et al., 2019) or the mean at week 12 in an internet-based CBT treatment study for people with BDD ($d=1.02$; Enander et al., 2016). More generally, large effect sizes for CBT vs. waitlist are to be expected, based on meta-analysis by Ost and colleagues (2015) for the closely related disorder OCD, which found that the weighted mean effect size of CBT vs. waitlist control was Hedges $g=1.31$, 95%CI: [1.08, 1.55]. The anticipated drop-rate was based on the weighted mean of drop-out rates (14.4%) reported in three studies that examined the efficacy of CBT treatment in participants with BDD: one compared to waitlist ($n=36$, 19.4% drop-out at week 12; Wilhelm et al., 2014), one compared to SPT,

in person (n=120, 23.3% drop-out at week 24; Wilhelm et al., 2019), and one comparing internet-based CBT vs. SPT (n=94, 1.1% drop-out at week 12; Enander et al., 2016).

In the wake of the COVID-19 pandemic, various negative mental health states and stressors - including anxiety, worry, depression, loneliness, financial strain, and trauma symptoms - were likely to increase in the US population. Furthermore, the variability of these negative mental health states and stressors would have likely increased as multiple waves of the pandemic and state-wide measures of social interaction restrictions swept the nation in the foreseeable future. In response, we increased the planned sample size to a total n of 80 (40 per group) of participants who start treatment (i.e., those who are eligible and willing and able to participate); this increase was intended to be reflective of a decrease in the anticipated effect size from 0.90 to 0.81 (i.e., a 10% decrease of the anticipated effect size). The plan for and justification of the sample size increase was reviewed by the Institutional Review Board at MGB prior to implementation.

VII. RISKS AND DISCOMFORTS

A. Complications of surgical and non-surgical procedures

Not applicable

B. Drug side effects and toxicities

Not applicable

C. Device complications/malfunctions

If the app or supporting clinician/coach dashboard malfunctions or does not work for a period of time, the patient may be unable to use the app to receive treatment or communicate with their coach. Similarly, if the clinician/coach dashboard were inaccessible, the coach would not be able to communicate via the app with the patient. These risks could result in minor harms to users such as inconvenience or a delay in treatment. If device malfunctions resulted in the patient's in-app weekly questionnaire responses not being sent to the coach/clinician, this could result in a delay in clinical response to an elevated safety questionnaire. To mitigate risks of a temporary device malfunction, participants were given the study staff and investigators' contact information in the consent document. Thus, the clinical and study staff can communicate with the participant by phone call instead of through the app. As with in-person therapy, there are times when a therapy session gets cancelled and treatment, as well as weekly symptom assessments, were thus temporarily delayed. Likewise, in face-to-face therapy, a therapist may be temporarily out of reach at times (e.g., on vacation) and backup lines of communication (e.g., pager coverage by a colleague) were put in place in case of emergencies. Thus, device malfunctions that lead to temporary delays in accessing the app functionality are similar to risks associated with temporary delays in traditional face-to-face therapy. See also, "Minimizing of Risks and Safety Reporting" under "D. Psychosocial (non-medical) risks" for further description of protections in place.

D. Psychosocial (non-medical) risks

Participants may feel uncomfortable due to the sensitive nature of the questions they may be asked. Likewise, some participants may feel uncomfortable about having assessment sessions digitally recorded and reviewed by project staff (which is necessary for rater supervision as well as assessment of the reliability of ratings adherence and competence). Participants could experience an increase in symptoms or suicidal ideation related to the natural waxing and waning of BDD or other psychiatric (e.g., depression) symptoms. BDD can be associated with other psychiatric symptoms (e.g., depression, anxiety), as well as suicidal thoughts and behaviors, which may also change over time. Breach of confidentiality represents a potential risk. Finally, the treatment procedures, particularly the exposure

exercises, will potentially provoke some anxiety. As discussed below, we took precautions to ensure that these potential risks were minimized (see Adequacy of Protection Against Risks below).

Minimizing of Risks and Safety Reporting.

The following procedures were implemented to protect participants against risks:

1. Participants with active suicidal ideation at the screening assessment were excluded from participating (see Inclusion/Exclusion criteria). If a subject scored ≥ 21 on the QIDS-SR and/or >1 on the QIDS-SR item #12, the independent evaluator followed up with a phone evaluation within 24 hours and referred the participant to a higher level of care if clinically indicated. Suicidal ideation at screening was also measured using the C-SSRS (see Inclusion/Exclusion criteria), and if a potential participant scored ≥ 2 , a study clinician, PI, or independent evaluator conducted a risk evaluation with the participant and referred the participant to a higher level of care if clinically indicated.
2. Participants with severe major depressive disorder were excluded from participating (see Inclusion/Exclusion criteria).
3. A disclaimer that is accessible from the home page of the digital CBT program was presented to remind participants that if they were experiencing suicidal thoughts, they should seek professional help or go to the emergency room right away. Links to 911 and suicide hotline numbers were provided along with this disclaimer.
4. A general resources page was available on the app at all times to participants, which included a suicide hotline number.

Participants' clinical improvement or deterioration was assessed weekly via a participant-rated CGI-BDD collected via the app (or REDCap, in waitlist condition). Participants could be withdrawn from the study if their clinical condition deteriorated substantially. Deterioration was defined by a combination of (1) a rating of 6 (much worse) or 7 (very much worse) on the weekly, participant-rated CGI-BDD across 2 subsequent weeks and (2) PI judgment that remaining in the study was not in the participant's best interest. Of note, a single rating of 6 or 7 on the weekly, participant-rated BDD-CGI also triggered a notification to the clinician/coach via text message and email. In the case that a BA-level coach was notified that a participant's CGI indicates deterioration, they notified a doctoral-level clinician as soon as possible (and within 24 hours). A study clinician then followed up with a phone evaluation within 24 hours of the alert and referred the participant to a higher level of care if clinically indicated. After an initial alert for a participant, study clinicians could use clinical judgement when determining follow-up for additional alerts.

5. Ratings on the QIDS-SR item 12 (suicide item) were carefully monitored weekly via the app (or REDCap, in waitlist condition); a score >0 at any assessment triggered a pop up message to be presented to the patient within the mobile app reminding participants that if they were experiencing suicidal thoughts, they should seek professional help or go to the emergency room right away. Links to 911, as well as a national suicide hotline, were provided within this popup notification. A score >1 also triggered notification to the clinician/coach via text message or email. In the case that a BA-level coach was notified that a participant reported a score >1 , they notified a doctoral-level study clinician as soon as possible (and within 24 hours). A study clinician, PI, or independent evaluator then followed up with a phone evaluation within 24 hours of the alert and referred the participant to a higher level of care if clinically indicated. After an

initial alert for a participant, study clinicians could use clinical judgement when determining follow-up for additional alerts.

6. Participants could also be withdrawn if, in the judgment of the PI, remaining in the study posed a substantial risk to the participant or a higher level of care is needed.
7. Treatment through app-based CBT was supplemented with electronic communication with a study coach, who could answer questions and guide participants through the treatment as needed. See *In-App Coach Training and Qualifications*, above, for details.
8. The independent evaluator(s) were highly experienced, highly trained, and closely supervised.
9. [name] (the PI) was available, if necessary, to discuss the study, alternative treatments, or any concerns about the study with participants if requested by the participant, coaches, or raters.
10. The PI and her co-investigator and the participants' study coach were available to answer study questions via the app or phone. This was clearly communicated orally and in writing to study participants.
11. All participants were provided with referral resources.
12. The study coaches and raters (IEs) made every attempt to help participants feel comfortable when discussing sensitive material. Participants could skip questions on assessments that they were uncomfortable answering.
13. If exposure exercises suggested through the treatment app were too anxiety provoking, participants were able to do alternative exercises that caused less anxiety.
14. The CBT treatment initially emphasized cognitive restructuring, which we anticipated would be less anxiety provoking than exposure treatment alone and would make exposure more tolerable.
15. Technologists from Koa Health who conducted the technology feedback interviews were trained professional staff with experience conducting patient interviews. They received additional training (including a multi-day workshop) from our team (MGH OCD and Related Disorders Program) on CBT and issues of confidentiality. They completed CITI training.
16. Three clinical psychologists or researchers familiar with BDD were selected to serve as a Data Safety Monitoring Board, to review the study once a year.
17. Participants designated a relative or friend who could be contacted should the subject be unavailable and the investigator had concerns about the subject's well-being.

We anticipated that the above procedures would be effective in protecting study participants against potential risks.

Adverse event reporting:

See below: "Adverse event reporting guidelines"

E. Radiation risks

Not applicable

VIII. POTENTIAL BENEFITS

A. Potential benefits to participating individuals

Participants may benefit from the comprehensive diagnostic assessment with a BDD expert, from careful clinical monitoring, and by experiencing some relief from their BDD symptoms through the CBT app.

B. Potential benefits to society

If app-based CBT for BDD were efficacious, it would offer increased, cost-effective access to CBT for BDD, a treatment which is otherwise difficult to access.

IX. MONITORING AND QUALITY ASSURANCE

A. Sponsor-initiated monitoring

Decus Biomedical, Inc. were hired by Koa Health to serve as external study monitors. They visited MGH to provide feedback regarding ongoing study procedures and data quality.

B. Independent monitoring of source data

The PI had overall responsibility for study data and participant safety. All aspects of the study were conducted in accordance with the hospital's policy on confidentiality.

Paper research records were kept de-identified, in a locked file in a locked office at MGH. Self-report measures and some clinician administered measures were collected using REDCap. REDCap (Research Electronic Data Capture) is a free, secure, HIPAA compliant web-based application hosted by the Partners HealthCare Research Computing, Enterprise Research Infrastructure & Services (ERIS) group. Data collection projects rely on a study-specific data dictionary defined by members of the research team with planning assistance from Harvard Catalyst | The Harvard Clinical and Translational Science Center EDC Support Staff. The REDCap software allows researchers to design and implement study surveys for collecting, storing, retrieving, and manipulating data electronically. The iterative development and testing process results in a well-planned data collection strategy for individual studies. Web-based self-report measures rely on a study-specific data dictionary built by members of the research team. Once built, participants and study staff can enter data directly into REDCap surveys via any computer or tablet with standard web access and browsers. Participants entered survey responses directly into an electronic assessment form on subject-facing REDCap, and the responses were then transmitted and stored in the secured and confidential database. Each participant only had access to his or her own survey, but not any other survey data. All data was collected and stored in compliance with the Standards for Privacy of Individually Identifiable Health Information ("Privacy Rule") of the Health Insurance Portability Act of 1996 (HIPAA). Any data that was transmitted electronically was encrypted and password protected. This electronic data capture system precludes the need for subsequent data entry by staff, thus minimizing human error, and resulting in improved data integrity and quality. All users had defined roles and privileges pre-determined by the system administrator. Thus, the PI could determine the level of access for each study staff such that only a limited number of people had access to sensitive study data.

We anticipated that the above procedures would ensure the confidentiality and integrity of study data.

C. Safety monitoring

Three clinical psychologists or researchers knowledgeable about BDD were selected to serve as a Data Safety Monitoring Board, to review the study once a year when the study was actively enrolling. The PI had overall responsibility for monitoring the integrity of study data and participant safety. Procedures for

managing participant safety, including the monitoring of participants throughout the trial and response to clinical deterioration (as defined above) should it occur, are detailed above in “**Minimizing of Risks and Safety Reporting.**”

D. Outcomes monitoring

Adverse events and data completeness were monitored regularly throughout the trial as described above.

E. Adverse event reporting guidelines

Adverse event reporting:

Adverse events were reported per PHRC guidelines.

X. REFERENCES

Alliez, J., & Robion, M. (1969). Aspects psycho-pathologiques de la defiguration leur relation avec dysmorphophobie [Psychopathologic aspects of disfigurement; their relation to dysmorphophobia]. *Ann Med Psychol (Paris)*, 2, 479-94.

American Psychiatric Association. (2013). *Diagnostic and statistical manual of mental disorders* (5th ed.). Arlington, VA: Author.

Borkovec, T. D., & Nau, S. D. (1972). Credibility for analogue therapy rationales. *J Behav Ther Exp Psychiatry*, 3, 257-260.

Cash, T.F., & Henry, P.E. (1995). Women's body images: The results of a national survey in the U.S.A. *Sex Roles*, 33, 19-28.

Cook, R. J., & Farewell, V. T. (1996). Multiplicity considerations in the design and analysis of clinical trials. *J R Stat Soc Ser A Stat Soc*, 159(1), 93-110.

Devilly, G. J., & Borkovec, T. D. (2000). Psychometric properties of the credibility/expectancy questionnaire. *J Behav Ther Exp Psychiatry*, 31, 47-55.

Eisen, J. L., Phillips, K. A., Baer, L., Beer, D. A., Atala, K. D., & Rasmussen, S. A. (1998). The Brown Assessment of Beliefs Scale: reliability and validity. *Am J Psychiatry*, 155, 102-8.

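### The attrition-bias check compares dropouts with completers, which cannot show whether the week-12 BDD-YBOCS contrast survives dropout that depends on unseen week-12 scores

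*Combined protocol and SAP*

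**What the plan says.** The opening text of section VI (Biostatistical analyses) sets out the handling of dropout. Dropout, withdrawal and loss to follow-up are tabulated by reason and arm. Then: "Analyses were conducted to ascertain to what extent dropouts were nonrandom, and, if so, what factors were associated with dropout". The next sentence names the method for bias: "To evaluate potential attrition bias, study dropouts were compared to study completers". Nothing says what follows if dropout proves to be nonrandom.

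The primary analysis (section VI-C) is a mixed model with categorical time (baseline, mid-point, end of treatment), arm and their interaction. It is fitted to all randomised participants with at least one assessment and tested by the week-12 contrast. The missing-data assumption behind it is not stated.

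The one other fit of the model is the per-protocol repeat: "We repeated our GLMM analyses using the per protocol sample". That set requires both a baseline and a post-treatment assessment and excludes anyone who started prohibited treatment. The responder proportion also leaves out participants without week-12 data.

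Sections V and VI add a real safeguard: unless consent was withdrawn, people who left or were withdrawn were still asked to attend assessments and were paid for them.

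**The concern.** The primary contrast is at week 12. A likelihood-based mixed model estimates it without bias if, given arm and the scores already recorded, the chance of a missing week-12 score does not depend on what that score would have been. A comparison of dropouts with completers uses recorded variables only, so it has no bearing on that condition. A null comparison does not support the assumption, and a positive one shows which variables predict dropout without showing how far the estimate could move.

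The question is live in this design. One arm works through a self-directed app and the other waits for the same app, so reasons for leaving can plausibly differ by arm. If some app-arm participants leave because they are doing worse than their recorded scores suggest, the effect is overstated. The per-protocol repeat uses only people with week-12 data, so its agreement with the primary result would not test the assumption. At stake are the size of the reported Cohen's d and, if the observed effect is moderate, its significance.

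**Working it through.** **Inputs (section VI-D).** "The power model used a two-sided alpha=0.05"; "a power of 0.90, equal allocation of participants into both treatment arms"; "an anticipated effect size of 0.9", later revised through "a decrease in the anticipated effect size from 0.90 to 0.81"; and "We further assumed a drop-out rate of 15% by the end of treatment". The dropout figure is not split by arm.

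**Reproducing the plan's figures.** Two-sample t-test, two-sided 0.05, power 0.90:
- d = 0.90 needs 27 per arm; 27/0.85 = 31.8, so 32 per arm and 64 in total, as stated.
- d = 0.81 needs 34 per arm; 34/0.85 = 40 per arm and 80 in total, as stated.
- Weighted dropout: (36 × 0.194 + 120 × 0.233 + 94 × 0.011)/250 = 14.4%, as stated.

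The sample size is not in dispute.

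**Tipping shift.** Let d be the observed effect in SD (waitlist minus app), π the share of app-arm participants with no week-12 score, and k the amount in SD by which they are worse than the missing-at-random prediction. With the waitlist arm left unshifted:
- adjusted effect = d − πk
- SE = √(2/n), with n the number observed per arm
- significance is lost at k* = (d − 1.96 × SE)/π

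At 15% dropout n = 34, SE = √(2/34) = 0.2425 and 1.96 × SE = 0.475. For d = 0.81, k* = (0.81 − 0.475)/0.15 = 2.23. The 19.4% and 23.3% rows use two of the plan's source dropout rates; the second was measured at week 24.

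| Dropout | n observed per arm | d = 0.81 (planned) | d = 0.60 (assumed) | d = 0.50 (assumed) |
|---|---|---|---|---|
| 15% | 34 | 2.23 | 0.83 | 0.16 |
| 19.4% | 32 | 1.65 | 0.57 | 0.05 |
| 23.3% | 31 | 1.34 | 0.44 | 0.01 |

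**One concrete scenario.** If app-arm dropouts end like waitlist participants, k = 0.81 and the effect is 0.81 − 0.15 × 0.81 = 0.6885, about 0.69, which is 15% smaller. Then z = 0.6885/0.2425 = 2.84, p about 0.005, still significant.

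**Can the planned check detect the problem?** It was simulated with 40 per arm, no true effect, 15% dropout and 20,000 replicates. App-arm dropout was driven by the unseen week-12 residual and waitlist dropout was random. The baseline to week-12 correlation was assumed to be 0.5, and dropouts were seen at baseline only. With dropouts about 1.0 SD worse in that residual:
- the missing-at-random estimate and the completer estimate were both 0.149, against a true value of 0;
- type I error was about 10% for each;
- the dropout-versus-completer test on baseline rejected in about 5% of trials, which is its false-positive rate.

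Even for recorded differences the check is weak: 0.15 × 80 = 12 dropouts against 68 completers gives 35% power for a 0.5 SD difference.

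**Allowing for week 6.** The simulation above is unfavourable to the plan, because the primary model also uses week-6 scores. A second set placed 15% app-arm dropout after week 6, with assumed correlations of 0.5 with baseline and 0.6 to 0.8 between weeks 6 and 12. When dropout followed the week-6 score, a bias of about 0.08 to 0.13 SD with baseline only fell to about 0 once week 6 was used. When dropout followed the week-12 score, a bias of about 0.17 to 0.18 SD fell to roughly 0.09 to 0.15 SD.

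**The case against.** The strongest reply is that the plan is better protected than a bare reading of the dropout check suggests, and most of that reply stands.

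- A reader might infer that the mixed model gives app-arm dropouts the same benefit as those who stayed. It does not. For anyone seen at week 6, the implied week-12 value is conditional on that score, so visible non-response is largely allowed for. Those who leave before week 6, or whose course changes afterwards, remain exposed.
- A reader might infer that nothing planned could give a sign of informative dropout. The tabulation of reasons by arm could show app-arm departures for lack of benefit. It does not say how far the estimate would move.
- A reader might infer that the per-protocol repeat is offered as an attrition check. The plan ties only the dropout-versus-completer comparison to attrition bias, and the per-protocol set serves another purpose too, since it removes those who began prohibited treatment. The narrower point remains: it does not test the assumption.
- Stopping the app need not mean a missing week-12 score, because assessments after withdrawal were sought and paid for. The 15% may therefore overstate the share unobserved.
- Only app-arm shifts are worked through above. If waitlist dropouts also did worse than predicted, the bias would shrink or reverse.

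None of this supplies an analysis that departs from missing at random.

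**Conclusion.** The concern holds in this limited form: the stated method for attrition bias cannot answer the question put to it, the assumption the primary model relies on is unstated, and no planned analysis varies it.

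The documents do not support the stronger conclusion that the primary result would be unreliable at the planned effect. At d = 0.81 and 15% dropout, a shift of 2.23 SD would be needed, and even 23.3% dropout needs 1.34 SD. The gap matters if the observed effect is nearer 0.5 to 0.6, if dropout is higher or unequal between arms, or when the size of the effect is what is being read, since 0.81 against 0.69 is a 15% difference.

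The tipping figures rest on a fixed standard error, a shift in the app arm only and equal dropout in both arms. The observed effects of 0.50 and 0.60, the correlations and the dropout mechanisms are assumptions. This is an improvement that should be made, not a defect that invalidates the trial.

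**What to change.** 1. State in section VI-C that the primary model assumes missing at random given arm and the recorded baseline and week-6 scores.
2. Keep the dropout-versus-completer comparison and the tabulation by reason and arm, presented as description and not as the test of attrition bias.
3. Add a delta-adjusted tipping-point analysis of the week-12 BDD-YBOCS contrast in all randomised participants. Vary the shift separately in each arm and report the combinations at which p reaches 0.05, with the adjusted estimates.
4. Optionally, add reference-based imputation of missing app-arm values from the waitlist arm as one named scenario.

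Section VI is written largely in the past tense and reports a finding on data transformations, so analysis appears to have been done. Label anything added after outcome data were seen as post hoc.

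The cost is some added wording and modest programming, with no new data and no change to the sample size. Reported robustness may look less favourable; if the observed effect is near the planned one, the analysis would support the result.
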